11.2. Sample Size Considerations

The sample size calculations are based on the primary outcome of cure rate at 4 weeks. Cure rate is defined as the proportion of individuals who are uninfected at the follow-up, where infection will be assessed using parasitological methods. The null hypothesis is that cure rate at 4 weeks is the same between children who received 40 mg/kg praziquantel and children who received 80 mg/kg praziquantel. The null hypothesis will be tested using a chi-squared test statistic. The analysis population will be comprised of all participants as randomised, regardless of whether or not they received the allocated treatment (intention-to-treat).

Data from Uganda found cure rates for *S. mansoni* infected 3-9 year olds of 70% and 82% for 40 mg/kg and 60 mg/kg praziquantel, respectively. We anticipate that cure rates may be lower in younger children and that the 80 mg/kg dose will have a higher cure rate than the 60 mg/kg. However, we conservatively power the trial to detect a difference in cure rate of 70% versus 82%. Using a two-sided 5% significance level, approximately 173 children per trial arm will be required for 80% power and 232 per arm (N=464) for 90% power to detect a difference in cure rate at 4 weeks between the trial arms. Allowing for loss to follow-up of 7%, a total of approximately 500 children will be required. A sample size of 600 will allow us adequate power to examine sub-groups such as younger (12-30 months) versus older (30-47 months) children, particularly given that the effect size is likely to be larger based on a higher dose (80 mg/kg).

This sample size will give 80% power to detect differences in the secondary morbidity outcomes measures. We increase the estimated loss to follow up for these endpoints given they occur at six and 12 months following treatment. With 10% attrition, we will have 540 subjects at the 12 month follow up. As one example of the effect size we will detect for the key secondary outcome of weight-for-height z-score at 12 months, we will have 80% power to detect a difference in mean weight-for-height z-score between the six-monthly and 12-monthly dosing groups as low as 0.24 z-score, assuming a standard deviation of 1 and two-sided significance level 5% between children who received six-monthly praziquantel (either 40 mg/kg or 80 mg/kg) and children who received 12-monthly praziquantel (either 40 mg/kg or 80 mg/kg). A weight for age z-score difference of 0.23 is biologically relevant, particularly based on mitigation of only one cause of nutritional morbidity in this setting. For hemoglobin, we will be able to detect a difference of 0.29 g/dL using a standard deviation of 1.2, power of 80%, and functional sample size of 540.

For the PK study, 137 children from both sites (Uganda/Philippines) will be sampled. These are the numbers needed for 80% power to show a slope of the relationship between log CAA at 24 days and AUC is significant to $p < 0.05$. We will include 150 children to allow for loss to follow-up and enable sufficient power.

To assess immunological responses, assuming an SD of 0.9, the sub-study would require a sample size of 104 to achieve 80% power at 5% significance level for detecting difference in mean of $0.35\log_{10}$ cytokine response between the groups. We will recruit 150 children to allow for attrition.

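### Section 11.2 gives 173 and 232 children per dose group, but its own inputs (70% v 82%, two-sided 5%) need 198 and 265; the planned 600 still suffices

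*Combined protocol and SAP*

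**What the plan says.** Section 11.2 fixes every input to the calculation:

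- **Rates.** Ugandan data are cited as showing "cure rates for *S. mansoni* infected 3-9 year olds of 70% and 82% for 40 mg/kg and 60 mg/kg praziquantel, respectively". The plan then says "we conservatively power the trial to detect a difference in cure rate of 70% versus 82" per cent.
- **Level.** "Using a two-sided 5% significance level". Section 11.1 also words the alternative as a difference in either direction.
- **Test.** "The null hypothesis will be tested using a chi-squared test statistic". No continuity correction is mentioned.
- **Allocation.** Table 1 has four arms of 150. Two arms share each baseline dose, so the comparison is 300 v 300.

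From these it concludes that "approximately 173 children per trial arm will be required for 80% power and 232 per arm (N=464) for 90% power". It goes on: "Allowing for loss to follow-up of 7%, a total of approximately 500 children will be required". It closes with "A sample size of 600 will allow us adequate power to examine sub-groups", giving younger v older children as the example. It supports this by expecting a larger effect at the higher dose, but gives no subgroup effect size or power.

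**The concern.** These are the design figures for the primary outcome, and the stated inputs do not reproduce them. If the per-group sizes are too small, the stated powers of 80% and 90% are too high and the total of about 500 is too low. A reader of section 11.2 would also see 600 as roughly 100 children more than needed, and would take that surplus as what pays for the subgroup analyses.

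**Working it through.** **1. Required size.** Write p1 = 0.70, p2 = 0.82, d = 0.12 and mean rate 0.76. The usual formula for an uncorrected chi-squared test, per group, is

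n = [z(α/2)·√(2·0.76·0.24) + z(power)·√(0.70·0.30 + 0.82·0.18)]² / d²

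The two square roots are 0.6040 and 0.5980.

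- 80% power: (1.960·0.6040 + 0.8416·0.5980)² / 0.0144 = 197.7, so **198**.
- 90% power: (1.960·0.6040 + 1.2816·0.5980)² / 0.0144 = 264.1, so **265** (530 in total).

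**2. Other two-sided variants for 70% v 82%.**

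| Method | 80% power | 90% power |
|---|---|---|
| Stated in section 11.2 | 173 | 232 |
| Chi-squared, uncorrected | 198 | 265 |
| Unpooled variance | 195 | 261 |
| Arcsine | 196 | 263 |
| Chi-squared, continuity-corrected | 214 | 281 |

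The smallest of these is still 12 to 13% above the stated figures, so rounding does not explain the gap.

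**3. Power at the stated sizes.** Power = Φ{[d·√n − 1.960·0.6040] / 0.5980}.

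- n = 173: Φ(0.660) = **74.5%**, stated as 80%.
- n = 232: Φ(1.077) = **85.9%**, stated as 90%.

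**4. Total after 7% loss.** The plan's own figure follows from its own start: 464/0.93 = 499, or about 500. That total leaves 500·0.93/2 = 232.5 per group and 86.0% power. The 90% requirement is 530/0.93 = **570**. With continuity correction it is 562/0.93 = 605.

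**5. Power at the planned 600.** 600·0.93/2 = 279 per dose group. Power = Φ(1.372) = **91.5%**. The margin over the 90% requirement is 600 − 570 = 30 children, against 600 − 500 = 100 as the text implies.

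**6. What would reproduce 173 and 232?** Several calculations come close:

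| Calculation | 80% power | 90% power |
|---|---|---|
| 70% v 82%, one-sided 5%, continuity-corrected | 171.8 | 231.4 |
| 74% v 86%, two-sided, uncorrected | 173.2 | 231.4 |
| 61% v 75%, two-sided, uncorrected | 173.1 | 231.2 |

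Each contradicts something that section 11.2 states: the first its sidedness, the other two its rates. The documents name none of them as the source.

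**7. Subgroups (a separate check).** The plan does not give the age split, so I assume two equal bands: 600·0.93/4 = 139.5 per dose group per band.

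- Within a band, 70% v 82%: Φ(0.390) = **65%**.
- Within a band, 70% v 84%: about 80%. For 70% v 85%: 85%.
- Interaction, for illustration, with 70% v 82% in one band and 70% in both dose groups in the other, on the risk-difference scale: SE = √[(0.21 + 0.1476 + 0.21 + 0.21)/139.5] = 0.0747. Power = Φ(0.12/0.0747 − 1.960) = **36%**.

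**The case against.** The strongest reply is that nothing in the trial changes. The plan enrols 600, not 464 or 500, and 600 exceeds the correct requirement for 90% power. That stands, and it limits the severity. A reader might infer from the wrong per-group sizes that the primary comparison is underpowered; the plan's own total does not support that. Only a continuity-corrected test would put the 90% requirement (605) slightly above 600, and the plan mentions no such correction.

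A reader who finds that 74% v 86% fits might also conclude that the wrong pair of rates was entered. The documents do not support that. The pair appears nowhere in them, and a one-sided continuity-corrected calculation with the plan's own rates fits about as well. The origin cannot be settled from the text. The error does not depend on it, because each explanation contradicts the stated inputs.

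On subgroups, the reply is that the claim is tied to 600 children and to an expected effect larger than 12 points. That is fair: an effect of 14 points within a band reaches about 80%. It would also be wrong to present the subgroup weakness as a result of the arithmetic error, since power within a band at 12 points would be 65% even if 173 and 232 were right. What remains is that section 11.2 calls the power adequate without giving a figure or the effect assumed.

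**Conclusion.** The figures of 173, 232 (464 in total) and about 500 in section 11.2 are wrong for the inputs stated beside them. The correct figures are 198, 265 (530 in total) and about 570. The stated sizes carry 74.5% and 85.9% power. This rests only on inputs that the plan gives, with the uncorrected chi-squared test and the whole 5% level available at the final analysis.

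The planned 600 gives about 91.5% power for the primary comparison, so the consequence is a misstated margin (about 30 children rather than 100) and not a trial that is too small.

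The subgroup remark is secondary. The 65% rests on an even age split and 7% loss. The 36% rests further on a chosen pattern of effects and on the risk-difference scale, because section 11.4 asks for interaction terms in regression models without naming a scale. Severity: should-fix.

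**What to change.** In section 11.2, and in the formal SAP that section 11.4 says will follow before database lock:

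1. Replace the per-group sizes with 198 (80% power) and 265 (90% power, 530 in total), and the inflated total with about 570.
2. State that the planned 600, less 7%, gives 279 per dose group and about 91% power, and that no continuity correction is used.
3. Say per dose group rather than per trial arm, since the trial has four arms.
4. Replace the unquantified subgroup claim with a figure and its assumptions, such as about 65% within an equal age band for 70% v 82%, reaching about 80% only at 70% v 84%. Add that the interaction tests in section 11.4 have much lower power (about 36% in the 12 v 0 point illustration), and label the subgroup results exploratory.

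The cost is wording only. Enrolment, allocation and the primary test stay as they are.

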1. *Screening* We propose to employ a two stage screening process. The first phase is a village - based survey to identify children who are infected using rapid point of care testing (urine Circulating Cathodic Antigen (CCA)). CCA provides a highly sensitive and efficient means to screen children, with high sensitivity demonstrated in young children.^{18,19 20,21} Two stool samples (taken on consecutive days) will also be collected from every child who is CCA positive prior to the start of the study, at four weeks +/-1 week after treatment, and at 12 months post-treatment to provide a measure of infection intensity. Fecal smears will be prepared from each sample in duplicate applying the thick Kato-Katz technique for the detection of *S. mansoni*, *S. japonicum* and soil-transmitted helminths. Mean egg counts per gram of stool (epg) will subsequently be calculated and three intensity categories will be considered for *S. mansoni* and *S. japonicum* infection: light (1-99 epg), medium (100 – 399 epg) and heavy (>400 epg) as per World Health Organization Guidelines.²²

The second phase of screening will occur at the field laboratories in Palo, Leyte, The Philippines and in Lake Albert, Uganda. Prior to study enrollment, each child will undergo a physical exam and medical history to determine eligibility. Children who are not eligible based on severe malnutrition (WHZ < -3.0), severe anemia (hemoglobin < 7.0 g/dL) or chronic medical condition as defined by a disease lasting longer than three months and impacting a child's daily function or normal activities will be excluded at this stage.²³

1. *Study visit 1/Baseline.* After determination of eligibility, subjects will be enrolled following all screening assessments. Both field stations have a patient intake area with private areas for consenting and physical examinations. At this visit, a small blood drawing catheter will be placed to minimize the number of times children need to have a needle stick. Blood will be drawn for baseline morbidity studies (5 ml). In depth measures of nutritional status will be made, and children will be randomized to receive either 40 mg/kg or 80 mg/kg of Praziquantel either annually or six-monthly (4 arms).

In addition, children will be randomly split into two groups, half will have an extra 7 ml of blood drawn at the time of the morbidity studies (N=150) for immunologic studies and half will take part in pharmacokinetic studies (N=150, further details below).

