11. STATISTICAL CONSIDERATIONS

11.1. Study Hypotheses

Primary outcome

The null hypothesis that there is no difference in cure rate assessed by microscopy at 4 weeks between children who received 40 mg/kg praziquantel and children who received 80 mg/kg praziquantel. This will be tested against the alternative hypothesis that there is a difference in cure rate at 4 weeks between children who received 40 mg/kg praziquantel and children who received 80 mg/kg praziquantel, and will be a superiority comparison.

Secondary outcomes

All secondary outcomes will be superiority comparisons, with alternative hypothesis of a difference in the outcome between the two sets of participants being compared.

For outcomes 1 to 5 below, the null hypothesis is that there is no difference in the outcome between children in the 40 mg/kg praziquantel group and children in the 80 mg/kg praziquantel group.

1. Mean egg reduction rate at 4 weeks
2. Schistosomal antigenic clearance assessed by CCA at 4 weeks
3. Schistosomal antigenic clearance assessed by CAA at 4 weeks
4. Prevalence of any adverse event within 3 hours of dosing

Adverse events will be classified by type. Adverse event types that occur with overall prevalence >5% or at prevalence >5% in either setting will also be tested for differences between trial arms.

5. (a) Prevalence of adverse event type 1 within 3 hours of dosing
(b) Prevalence of adverse event type 2 within 3 hours of dosing
(c) Prevalence of adverse event type 3 within 3 hours of dosing
continued for all adverse event types occurring with prevalence >5%

For secondary outcomes 6 to 13 below, two null hypotheses will be tested. The first null hypothesis is that there is no difference in the morbidity outcomes between children who received six-monthly praziquantel (either 40 mg/kg or 80 mg/kg) and children who received 12-monthly praziquantel (either 40 mg/kg or 80 mg/kg). The second null hypothesis is that there is no difference in the morbidity outcomes between children who received 40 mg/kg praziquantel (regardless of dosing schedule) and children who received 80 mg/kg praziquantel (regardless of dosing schedule).

6. Mean weight-for-height z-score at 12 months
7. Proportion with weight-for-height z-score at 12 months < -2
8. Mean MUAC-for-age z-score at 12 months
9. Proportion with MUAC-for-age z-score at 12 months < -2
10. Mean height-for-age z-score at 12 months
11. Proportion with height-for-age z-score at 12 months < -2

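### The immunology sub-study's sample size of 104 is a per-group figure: if its 150 children form two equal groups, power for 0.35 log10 is about 61–66%, not 80%

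*Combined protocol and SAP*

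**What the plan says.** Section 11.2 (Sample Size Considerations) gives the calculation in two sentences. The inputs are "To assess immunological responses, assuming an SD of 0.9", a difference in means of 0.35 on the log10 scale, and a comparison of "cytokine response between the groups". The result is that "the sub-study would require a sample size of 104 to achieve 80% power at 5% significance level". The recruitment plan follows: "We will recruit 150 children to allow for attrition".

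Section 4.2.1, under Study visit 1/Baseline, confirms that 150 is the whole subset: "half will have an extra 7 ml of blood drawn at the time of the morbidity studies (N=150) for immunologic studies". The visit descriptions in section 4.2.1 and sections 7.5 and 7.6 refer to the same 150 children at follow-up. Section 7.3 places the sub-study in Uganda.

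The plan does not say which groups are compared, whether this test is one- or two-sided, or what attrition is expected. Section 11.4 describes no analysis for the immune responses. Section 11.1 lists them as exploratory (item 15), under a general statement that secondary outcomes are tested "with alternative hypothesis of a difference in the outcome between the two sets of participants being compared".

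**The concern.** Recruiting 150 to protect a requirement of 104 makes sense only if 104 is the total. The two-sample formula gives 104 as the size of each group, so a factor of two appears to have been lost. The neighbouring calculations in section 11.2 keep the two apart: the cure-rate paragraph gives 232 per arm with a total of 464, and the 0.24 z-score and 0.29 g/dL differences reproduce with 270 per group out of 540.

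What is at stake is the accuracy of the power claim. Children aged 12–47 months in this subset give an extra 7 ml of blood at baseline, 4 weeks, 6 months and 12 months, and those who approve that sampling are told it buys 80% power for a stated difference.

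**Working it through.** **Inputs.** From section 11.2: SD 0.9, difference 0.35 log10, 5% significance, 80% power, 150 children recruited. Two-sided testing is taken from the non-directional alternative in section 11.1 and from the two-sided 5% level used elsewhere in section 11.2. Equal groups are an assumption. It fits Table 1, which has about 75 children per arm per site: half of each Ugandan arm gives about 37.5, and two pooled arms give 75.

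**Reproducing the plan's figure.** For two independent means, 1:1:

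n per group = 2 × (1.960 + 0.842)² × (0.9 / 0.35)² = 103.8, rounded up to 104. The total is 2 × 104 = 208. The noncentral t version gives 104.8, or 105 per group.

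So 104 is reproduced, as a per-group number. As a between-group total it is not:

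- one-sided 5%: 82 per group, 164 in total;
- 2:1 allocation: 234 in total;
- 3:1 allocation: about 280 in total.

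**Power with the planned 150** (two-sided t test, equal groups, standardised difference 0.35 / 0.9 = 0.389):

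| Evaluable children | Per group | Power |
|---|---|---|
| 104 | 52 | 50% |
| 150 × 0.90 = 135 | 67.5 | 61% |
| 150 × 0.93 = 139.5 | 69.75 | 63% |
| 150 | 75 | 66% |
| 208 | 104 | 80% |

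The 7% and 10% loss rates are those section 11.2 uses for the 4-week cure rate and the 12-month outcomes.

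**Detectable difference at 80% power** = (1.960 + 0.842) × 0.9 × √(2/n):

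- n = 75: 0.41 log10;
- n = 67.5: 0.43 log10 (0.44 with the t distribution).

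**Children needed for the stated power.** 208 / 0.93 = 223.7, so 224 with 7% loss; 208 / 0.90 = 231.1, so 232 with 10% loss.

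**Other contrasts.** One arm against another (about 37.5 each) gives about 38% power with no loss. A one-sided 5% test on 75 per group gives 77%, still short of 80%.

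**Baseline adjustment.** With the baseline response as a covariate, the requirement falls to 104 × (1 − r²) per group, where r is the baseline/follow-up correlation. Meeting it with 75 per group needs r² ≥ 1 − 75/104 = 0.279, so r ≥ 0.53. With 67.5 per group it needs r² ≥ 1 − 67.5/104 = 0.351, so r ≥ 0.59.

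**The case against.** The strongest reply is that 104 can be a legitimate total. If each child's follow-up response is compared with his or her own baseline, the SD is 0.9 at each visit and the two measurements are uncorrelated, the variance of the change is 2 × 0.9² and the requirement is again 103.8, now 104 children in all. The 150 would then give about 92% power, or 89% after 10% loss. The objective concerns responses to infection and treatment, and the same children are bled repeatedly, so the design could support such a comparison. It follows that the number 104 alone does not prove a per-group reading, and a reader who inferred that no other reading can produce it would be wrong. But the paired reading contradicts the sentence itself, which refers to a difference between groups, and it needs zero correlation within a child. If 0.9 were instead the SD of the change, the paired requirement would be 52.

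A second reply is that the contrast might be infected against uninfected children, since section 7.3 also recruits a subset without schistosomiasis. With all 150 infected children in one group, power would be about 79% with 75 controls and 85% with 100; both control numbers are assumptions. Section 7.3 assigns those children's samples to gut microbiota, EED and morbidity markers, not to the immunology assays, and gives no number, so this reading has little support.

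Three limits stand. The groups are undefined, so any power figure is conditional. The attrition rates are borrowed. And immune responses are labelled exploratory.

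**Conclusion.** On the plan's own inputs and its own description of a between-group comparison, 104 is the number per group and 208 evaluable children are needed. If the 150 children form two equal groups and the test is two-sided, power for 0.35 log10 is about 66% with no loss and about 61% with 10% loss, against the stated 80%. The shortfall remains with no attrition, and also with a one-sided test.

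Two stronger conclusions might be inferred, and neither is supported. The first is that the trial is underpowered: the cure-rate and morbidity sample sizes do not depend on this calculation. The second is that a null cytokine result will be taken as evidence of no effect: nothing in the documents plans that inference. This is a should-fix correction to an exploratory sub-study.

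**What to change.** In section 11.2:

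1. Name the groups (for example 40 against 80 mg/kg, or six-monthly against 12-monthly), the time point, the two-sided 5% test and the attrition assumed.
2. Restate the requirement as 104 per group, 208 evaluable in total.
3. Keep 150 children and state what they give: about 61–66% power for 0.35 log10, or 80% power for about 0.41–0.44 log10.

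In section 11.4, add an analysis of follow-up responses with the baseline cytokine response as a covariate, as that section already does for anthropometry and anemia. This should improve precision, but it reaches 80% power only if the baseline/follow-up correlation is about 0.53 (no loss) to 0.59 (10% loss) or more. The documents give no correlation and treatment falls between the two measurements, so the gain should not be written into the power claim.

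The cost is a few sentences and one model covariate. No extra children or blood are required. If a paired comparison was intended after all, the sentence should say so and state the within-child correlation or the SD of the change.

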11.3. Planned Interim Analyses

11.3.1. Interim Safety Review

Given that the study population is vulnerable the project will require rigorous independent oversight by a data safety and monitoring board (DSMB). DSMB membership will be independent of the trial with input from investigators; we anticipate that it will comprise experts on schistosomiasis and child health, and a statistician with experience of trials in LMICs. The frequency of meetings and other procedural issues will be overseen by the study sponsor.

The DSMB will regularly monitor all data to consider any potential harm to participants. Formal rules for stopping due to harm will be discussed with the DSMB at their first meeting. An interim analysis will be performed on the primary outcome when approximately 20% of children have been randomised. Only the DSMB and the trial statistician will be unblinded for this interim analysis.

The DSMB will meet once three months after study enrollment begins and then every six months during enrollment.

